## PROTOCOL

### Study Title

Varenicline for the treatment of postural and gait dysfunction in Parkinson Disease (PD).

### Objectives

To determine if varenicline is effective for abnormalities in balance and posture in PD.

### Design and Outcomes

The design is a randomized, double-blinded, placebo-controlled study conducted at one center. The primary outcome is the change in the Berg Balance Scale. Secondary outcomes include the Activities-specific Balance Confidence Scale, Parts I-III of the MDS-UPDRS, the Timed up and go test, the Folstein Mini Mental Status Exam (MMSE), the Beck Depression Inventory, the Beck Scale for Suicidal Ideation, the Frontal Assessment Battery (FAB), and total number of falls.

### Interventions and Duration

Subjects will be randomized to placebo or varenicline with an escalation phase of one week (0.5 mg daily for three days, 0.5 mg twice daily for four days, then 1 mg twice a day to begin at week two). The rating scales will be performed before initiation of the drug, and then the subject will remain on drug for eight weeks after which outcomes will be reassessed.

### Sample Size and Population

Sample size is estimated to be 38 patients; however 42 will be recruited to allow for attrition. All patients will have been diagnosed with PD using the UK Brain Bank Criteria. There will be no stratification of randomization.

## STUDY OBJECTIVES

### Primary Objective

The hypothesis tested is that varenicline will result in improvement of balance and postural instability after eight weeks of treatment compared to placebo. The null hypothesis is that there will be no difference in tests of balance between subjects on placebo compared to those on varenicline using the Berg Balance Scale as the primary outcome. The primary and secondary outcomes will be performed by the site investigator who will be blinded to treatment.

### Secondary Objectives

There are two secondary hypotheses. First, we hypothesize that subjects with the postural-instability-gait disturbance (PIGD) subtype of PD will be more responsive to treatment compared to the tremor-predominant subtype. Patients will be categorized with tremor-predominant PD if the ratio of the mean tremor score to the mean PIGD score is 1.5 or higher and as PIGD predominant if the ratio is 1 or lower. The mean PIGD score

will be defined as the sum of an individual's baseline falling, freezing, walking, gait and postural stability UPDRS scores divided by five.

The second hypothesis is that varenicline will improve cognitive functioning in PD subjects. This hypothesis will be tested by comparing the results from the MMSE and the FAB at the beginning of the study, at four weeks, and at eight weeks.

## BACKGROUND

### Rationale

Parkinson disease (PD) is a clinical entity characterized by bradykinesia, rigidity, tremor, and postural instability. Current treatments primarily focus on replacement of dopamine to compensate for the degeneration of the substantia nigra pars compacta dopaminergic neuronal population. Though dopamine treats many of the motor symptoms of PD, postural instability (which often leads to falls) typically is least responsive to therapy. PD affects 2,000,000 people in the United States. It affects 49.7 per 100,000 person-years for those over age 50. The incidence of falls is estimated to be as high as 69% in PD patients. Clearly falls in this population can lead to significant sequelae of fractures, prolonged hospitalization, and associated medical complications.

Varenicline (Chantix) is a novel partial  $\alpha 4\beta 2$  agonist and full  $\alpha 7$  agonist developed as an aid for smoking cessation and has been shown in initial studies to improve imbalance in patients with inherited spinocerebellar ataxia. Recently, the degeneration of the cholinergic system arising from the pedunculopontine nucleus (PPN) in the brainstem has been implicated in gait dysfunction in PD. Striatal cholinergic inputs are supplied from the PPN both via the intralaminar complex of the thalamus and through direct inputs. The primary subtypes of cholinergic receptors present in the striatum are nicotinic and include  $\alpha 4\beta 2$ ,  $\alpha 6\beta 2$ , and  $\alpha 7$  receptors. Varenicline has been reported in case reports to be effective in ataxia for patients with Spinocerebellar Ataxia types 3 and 14, the Fragile-X Associated Tremor/Ataxia syndrome (FXTAS), as well as improving subjective proprioception in Friedreich's Ataxia. Varenicline was given at 1mg twice a day and showed improvement on the Scale for the Assessment and Rating of Ataxia (SARA) scale. Other medications used for balance and prevention of falls in PD have not been shown to be helpful and thus the mainstay of treatment involves physical therapy.

The dosage escalation medication regimen in this protocol is similar to those studies conducted for smoking cessation and for ataxia. The active medication will be dosed twice daily (1 mg BID) due to convention, though the half-life of the drug is listed as 24 hours. A week of dose escalation will allow for maximal tolerability. The worsening of neuropsychiatric symptoms reported in some patients with other disorders on varenicline appears to be isolated in patients with prior psychiatric conditions, but this has not always been the case. In order to monitor for this potential side effect and to screen for potential sub-clinical depression, the Beck Depression Inventory will be given to all subjects and followed during the course of the study. Suicidal ideation and attempt has also been reported in patients taking varenicline, so the Beck Scale for Suicidal Ideation will also be administered to participants during the course of the study. There are no aspects of the proposed dosing schedule that are not FDA-approved for other indications. This study is

of high priority due to the absence of any proven medications to treat imbalance in this disorder.

### STUDY DESIGN

This is a randomized, double blind, placebo controlled parallel-designed study. Varenicline was chosen because of its novel mechanism of action and its preliminary success in treating some forms of hereditary ataxia. This will be the first clinical trial testing varenicline in patients with Parkinson Disease. The specific nicotinic cholinergic receptors varenicline targets are located in the human striatum with afferent cholinergic input arising from the brainstem where the locomotor center of the brain is thought to originate. The direct and indirect effects on these receptors may provide a mechanism to improve postural instability and imbalance in this patient population.

### SELECTION AND ENROLLMENT OF SUBJECTS

Inclusion criteria:

- Subjects will be diagnosed with Parkinson Disease (PD) by the UK Brain Bank criteria.
- Subjects will have to be at least stage 2 on the Hoehn and Yahr staging system of PD and have a history of at least 1 fall or near fall in the last 6 months.
- Subjects must have a stable medication regimen.
- All subjects will be over the age of 40 in an attempt to exclude inherited forms of parkinsonism.
- Serum creatine kinase, complete metabolic panel, complete blood count, liver function tests, renal function tests, platelets and EKG are within normal limits (results obtained from primary care physician and dated within the past 6 months or obtained at screening visit).

Exclusion criteria:

- Hoehn and Yahr stage 5 subjects.
- Subjects with a history of major psychiatric disorder, deep brain stimulation surgery, recent cerebral trauma, cardiac arrhythmia, or renal insufficiency.
- a cardiovascular procedure in the last 5 years (eg, percutaneous transluminal coronary angioplasty) or have cardiovascular instability (including myocardial infarction or unstable angina). Other cardiovascular exclusions include uncontrolled hypertension, significant neurological sequelae of cerebrovascular disease, peripheral vascular disease with prior amputation, or severe congestive heart failure (New York Heart Association class III or IV). Concurrent treatment with any MAOIs, bupropion (Wellbutrin), or nicotine patches.
- Dementia or other psychiatric illness that prevents the patient from giving informed consent (MMSE score less than 25).
- Concurrent treatment with trihexyphenidyl (Artane) or benzotropine mesylate (Cogentin).
- Significant degree of dysphagia, by history.

- Legal incapacity or limited legal capacity.
- Presence of severe renal disease (BUN 50% greater than normal or creatinine clearance <60 mL/min) or hepatic disease.
- Abnormal creatine kinase and/or platelet count in the past 6 months (as determined by lab reports obtained from primary care physicians or conducted at baseline).
- Use of varenicline within the previous 30 days.
- Women of childbearing potential who are pregnant at the time of screening or who will not use adequate contraception during participation in the study.
- Allergy/sensitivity to the drug or its formulations.
- Concurrent participation in another clinical study.
- Active substance or tobacco use or dependence.
- moderate or severe chronic obstructive pulmonary disease
- Serious illness (requiring systemic treatment/or hospitalization) until the subject either completes therapy or is clinically stable on therapy, in the opinion of the site investigator, for at least 60 days prior to study entry.
- Inability or unwillingness of the subject or legal guardian/representative to give written informed consent.

#### Study Enrollment Procedures

Patients with Parkinson Disease (PD) will be recruited through the Movement Disorders clinic located at the Neuroscience Institute at Rush University Medical Center. There are eight movement disorders attending physicians and three fellows who see approximately 4800 new and follow-up PD patients per year. Recruitment goals are expected to be predominantly achieved through the cohort of individuals seen at Rush, but advertising may also be conducted through monthly PD support group meetings or newsletters to enhance enrollment. Potential subjects may be identified by their treating physician in the Movement Disorders Clinic at Rush or referred to Rush from elsewhere. If a patient is interested in enrolling in this study, he/she will be invited to an initial study visit, at which time he/she will provide informed consent after a full explanation of the study.

Documentation of inclusion and exclusion criteria will occur if the patient is interested in enrollment. Eligible subjects who refuse participation will be given the option of later enrollment if desired.

Much of recruitment will occur from physicians who have a treatment relationship with the patient. Prior to the consent process, the Mini Mental State Examination will be performed to determine the patient's level of comprehension. If the potential subject scores less than 25, the patient will be excluded from the study. Consent will be obtained by the primary investigator and the potential subject. All investigators are trained in the conduct of human research. A copy of the consent form will be provided to all subjects.

The independent medical monitor will be responsible for obtaining group assignments. The assignment will be masked to the PI, the treating physician, the

subject, and all other staff conducting the study. The medical monitor will be responsible for correct drug dispensing for each subject based on randomization.

## STUDY INTERVENTIONS

### Interventions, Administration, and Duration

42 subjects will be randomized to receive 1 mg twice daily of oral varenicline or matched placebo. The therapeutic dose will be escalated over the first week as 0.5 mg daily for three days, and then increased to 0.5 mg twice daily for the next four days. Thereafter, subjects will continue on 1 mg twice daily for the remaining eight weeks. The outcome measures will be assessed at the end of week 5 and then repeated at the conclusion of the study. Side effects will be monitored at each of the encounters with the subject, either in person or by telephone. The most common expected side effects include nausea, insomnia, abnormal dreams, or headache. Subjects will be evaluated in the outpatient Movement Disorders Clinic at Rush University at the initiation and conclusion of the study. All patients may remain on other medications for neurologic signs (with the exception of those mentioned in the exclusion criteria), but the dose of these medications must remain stable during the duration of the study.

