### CLINICAL AND LABORATORY EVALUATIONS

#### Timing of Evaluations

Subjects will be consented and have initial laboratory studies and rating scales at the entry visit. Once on the study medication, they will be contacted by phone at three weeks for questions regarding side effects, clinical issues, and to answer any questions. The subject will be reassessed after five weeks for depression or suicidal ideation, and they will continue with the intervention or placebo. Again, they will be contacted by phone at week seven to assess for safety and tolerability. They will be seen at nine weeks and outcome measures will be performed.

Table 1. Timing of Evaluations

Evaluation	Screening	Entry	Week 3	Week 5	Week 7	Week 9
Informed Consent		X				
Documentation of PD	X					
Medical/Treatment Hx	X					
Inclusion/Exclusion	X					
Clinical Assessment		X				
Neurological Exam		X				
Adherence Assessments			X	X	X	X
Questionnaires						
MDS-UPDRS and other rating scales		X				X
Beck Depression/suicide scales		X		X		X
Mental Status exam		X				X
FAB		X				X
EKG		X				

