#### On-Study Evaluations

Blood chemistries, liver function tests, and hematology laboratory tests will be performed at two times during the study. Rating scales for movement disorders and cognitive disturbances will be performed twice during the study. The allowable time window is Schedule of Evaluations  $\pm$  7 days.

- Entry

The entry visit will occur at least two weeks after the screening visit to allow for adequate drug supply. Study drug will be dispensed at the entry visit.

- Intervention Discontinuation Evaluations

Evaluations done at the time of discontinuation include blood chemistry, hematology, and the rating scales. In addition, an adherence assessment will also be done.

- Post-Intervention Evaluations

Neurological examinations will be performed according to the standard of care by the treating neurologist/investigator.

- Final Evaluations

The final visit will consist of blood chemistry and hematology, neurological examination, rating scales (BBS, MDS-UPDRS, TUG, ABC, MMSE, FAB, BDI, and BSSI), and adherence assessment.

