### Outcomes and Data Analysis

- Primary outcome (Aim 1): The primary hypothesis will be tested using a paired *t*-test using means of the total Berg Balance Scale score before and after treatment. Linear regression will be used to determine if there is an association among outcome, gender, age, race, or ethnicity. This outcome will be determined by the rating of patients from a blinded movement disorders neurologist.
- Secondary outcomes (Aim 2): Secondary hypotheses will be tested using paired *t*-tests on the full MDS-UPDRS, the TUG, and the ABC scale. For side effect analysis, logistic regression will be performed with the treatment arm as the dichotomous outcome and the MMSE and FAB as covariates. In addition, gender and age will also be included as covariates.
- Side effects (Aim 3): Adverse events will be recorded and classified as to seriousness of the side effect and likelihood that the side effect is related to the drug. Adverse events in the treated group versus the untreated group will be compared and any events that are significantly more frequent in the treated group will be identified.
- Sample Size and Accrual: Sample size was estimated using published means and standard deviations of the BBS in PD subjects. The mean of the rating scale is 40.22 with a standard deviation of 8.48. Based on a published effect size of a change of 8 points, and using a power of 0.80 and a significance of 0.05 with a two sided test, a sample size of 19 subjects for each group would be needed for a parallel design. To allow for attrition, 42 subjects will be recruited. Intent to treat analysis will be performed. The number of subjects lost to follow-up is likely to be low due to the relative lack of efficacy of other forms of treatment for this particular symptom of PD. Power for calculating secondary outcomes is lower than 0.8.

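### Mid-study MMSE and FAB ratings are missing from the visit schedule, no between-arm comparison of either is named, and the falls outcome has no definition, specified count or analysis

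*Combined protocol and SAP*

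**What the plan says.** **Cognitive ratings.** Secondary Objectives states that the second hypothesis is tested by "comparing the results from the MMSE and the FAB at the beginning of the study, at four weeks, and at eight weeks". Interventions, Administration, and Duration says: "The outcome measures will be assessed at the end of week 5 and then repeated at the conclusion of the study".

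Timing of Evaluations describes the mid-study contact differently: "The subject will be reassessed after five weeks for depression or suicidal ideation". Of the final visit it says: "They will be seen at nine weeks and outcome measures will be performed". Table 1 agrees with that text. The mental status exam, the FAB, and the row for the MDS-UPDRS and other rating scales are marked at Entry and Week 9. Week 5 carries adherence and the Beck scales only. On-Study Evaluations adds: "Rating scales for movement disorders and cognitive disturbances will be performed twice during the study". The synopsis says that "the subject will remain on drug for eight weeks after which outcomes will be reassessed" and mentions no interim rating.

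**Analysis.** The Aim 2 paragraph of Outcomes and Data Analysis plans paired t-tests "on the full MDS-UPDRS, the TUG, and the ABC scale". MMSE and FAB appear there only as covariates in a logistic regression introduced for side effects, in which treatment arm is the dependent variable.

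**Falls.** Design and Outcomes lists the number of falls among the secondary outcomes. The schedule, the list of final evaluations and the evaluation definitions specify no fall count, and the analysis section names no falls analysis.

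**The concern.** Site staff work from the visit schedule. If Table 1 is followed, no mid-study MMSE or FAB will exist, and the comparison promised in Secondary Objectives cannot be made. A baseline-to-Week-9 comparison would still be possible, but the analysis section does not set one out, so its form could be chosen after unblinding.

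The falls outcome is open in the same way. Nothing says what counts as a fall, over what period, or how falls are elicited. Eligibility treats a fall and a near fall alike, so the meaning cannot be taken from there. A count assembled afterwards from adverse-event notes would depend on how completely those notes were made, possibly differently by arm.

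**Working it through.** **1. The plan's own figure.** Inputs from Sample Size and Accrual: difference 8, SD 8.48, power 0.80, two-sided 0.05. Normal approximation: n = 2(1.96 + 0.84)²(8.48/8)² = 2 × 7.84 × 1.1236 = 17.6, so 18 per group. The two-sample t-test gives 18.65, so 19 per group, with power 0.808 at 19. The stated 19 is reproduced. It uses the Berg scale only; nothing in this point enters it.

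**2. Week numbering.** If Secondary Objectives counts from the end of the one-week escalation, 1 + 4 = Week 5 and 1 + 8 = Week 9. The allowed window of ±7 days would also cover a one-week offset. The labels four/eight and five/nine can therefore mean the same visits. The conflict lies in what is done at the mid-study contact.

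**3. Mid-study content, side by side.**

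| Section | MMSE and FAB at mid-study? |
|---|---|
| Secondary Objectives | Yes, both named |
| Interventions, Administration, and Duration | Yes, if outcome measures means all of them |
| Timing of Evaluations, text | No; depression and suicidal ideation only |
| Table 1 | No; Entry and Week 9 |
| On-Study Evaluations | Most naturally no: two ratings, with Entry under the same heading. Two post-baseline ratings is a possible reading |
| Interventions and Duration (synopsis) | Silent; does not exclude one |

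The prose and the table of Timing of Evaluations agree, so a damaged table does not explain the gap.

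**4. What losing Week 5 costs for cognition.** The documents give no between-visit correlation, so take r = 0.5 to 0.8 as an assumption, equal between all visits, with unit variance and adjustment for baseline.

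- Week 9 alone: variance factor 1 − r².
- Mean of Weeks 5 and 9: variance factor (1 + r)/2 − r².
- r = 0.5: 0.75 against 0.50, variance +50%, SE +22%.
- r = 0.7: 0.51 against 0.36, variance +42%, SE +19%.
- r = 0.8: 0.36 against 0.26, variance +38%, SE +18%.

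These losses arise only if the endpoint is the two-visit mean, which no section names. If the endpoint is Week 9 with complete data, the loss is about nil.

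**5. What a falls comparison could show.** Assumptions, none of them in the documents: μ = 0.5 to 4 falls per subject over nine weeks, dispersion k = 0.5 to 2, and share c of falls noted. With 19 per arm, SE(log rate ratio) = √[(2/(cμ) + 2k)/19].

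- Complete counts, μ = 4, k = 0.5: √(1.5/19) = 0.281; exp(1.96 × 0.281) = 1.73.
- Complete counts, μ = 0.5, k = 2: √(8/19) = 0.649; exp(1.96 × 0.649) = 3.57.
- Half of falls noted: the SE ratio runs from √(5/4.5) = 1.05 (μ = 4, k = 2) to √(9/5) = 1.34 (μ = 0.5, k = 0.5).
- 30% noted: from √(5.667/4.5) = 1.12 to √(14.333/5) = 1.69 at the same two corners.
- Unequal noting, for example 60% against 50%: the rate ratio is off by 0.6/0.5 = 1.2.

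**The case against.** Four objections have force.

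- **The week 5 statement in the interventions section is partly met.** Design and Outcomes lists both Beck scales as secondary outcomes, and Table 1 marks them at Week 5 and Week 9. A reader might infer that the statement is flatly contradicted. It is not: it is met for the Beck scales and unmet for the other scales. The firm conflict is with Secondary Objectives, which names MMSE and FAB.
- **Cognition is not wholly without a test.** A reader might infer that no test is planned. That is too strong. Secondary Objectives states a comparison over time, and the logistic model links MMSE and FAB to arm through their coefficients. But that model is labelled for side effects and gives no time point, change score or effect estimate, and the t-tests for the secondary hypotheses name three other scales.
- **Falls may be picked up in passing.** Special Instruction and Definitions of Evaluations calls for a review of safety, tolerability and effectiveness at every contact, with adverse events recorded on the CRF. Falls noted there would enter the Aim 3 comparison of arms. The CRFs and the Manual of Operations are not available, so the absence of a fall field is shown only for the protocol text. Still, no count is named there, and the UPDRS falling item is a score. Aim 3 commits to identifying events in excess on active treatment. It does not say that only those will be reported, but it states no report for a reduction.
- **Secondary power is already said to be below 0.8.** This limits what the results can show. It does not supply the missing schedule entry, count or analysis.

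**Conclusion.** The point holds for the secondary outcomes and should be corrected. The schedule does not provide the mid-study MMSE and FAB that the cognitive hypothesis calls for. The analysis section names no between-arm comparison of change in either scale. The falls outcome has no definition, no specified count in the protocol text and no analysis.

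A reader might infer that the trial loses substantial precision on cognition, or that its main result is weakened. The documents support neither. The 38% to 50% increase in variance depends on an endpoint that the plan does not name and on assumed correlations. The primary analysis and the 19 per group do not use these measures. The fall figures rest wholly on assumed rates, dispersion and capture. They show that even complete counts would give an estimate with a wide interval, and that partial or uneven recording would make it wider or shift it.

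**What to change.** 1. **Schedule.** Bring Secondary Objectives, the interventions section, Timing of Evaluations with Table 1, and On-Study Evaluations under one week numbering. Either (A) mark MMSE and FAB, and any other scale intended, at Week 5 in Table 1, amend the statement that ratings are done twice, and say whether week 5 is a clinic visit; or (B) correct Secondary Objectives and the interventions section to baseline and Week 9, keeping the Beck scales at Week 5. B is a text change. A means a longer week 5 contact, or an in-person one if it was meant to be remote, and one more exposure to the tests in both arms. The mode of that contact is not stated; the interventions section says only that "Subjects will be evaluated in the outpatient Movement Disorders Clinic at Rush University at the initiation and conclusion of the study".

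2. **Cognition analysis.** Add to Outcomes and Data Analysis a between-arm comparison of MMSE and of FAB at Week 9, each adjusted for its baseline, with Week 5 as supportive if collected. This costs text only.

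3. **Falls.** Define a fall as distinct from a near fall. Record the number since last contact at the existing week 3, 5, 7 and 9 contacts. Pre-specify a two-sided between-arm comparison of counts that allows for follow-up time, reported as a rate ratio with 95% CI and described as an estimate, not a powered test. The cost is one question and one CRF field at each of four contacts: 42 × 4 = 168 entries.
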